12 Month Post-Op Visit (± 8 weeks)	
 • Patient Assessment • Oswestry Disability Index (ODI) • Clinician Evaluation • Radiographs • Radiographic Assessment • Adverse Event (as needed) • Protocol Deviation (as needed) • Patient Discontinuation (as needed)
24 Month Post-Op Visit (± 8 weeks)	
 • Patient Assessment • Oswestry Disability Index (ODI) • Clinician Evaluation • Radiographs • Radiographic Assessment • Adverse Event (as needed) • Protocol Deviation (as needed) • Patient Discontinuation (as needed)
Annual Post-Op Visit (± 8 weeks)	
 • Patient Assessment • Oswestry Disability Index (ODI) • Clinician Evaluation • Radiographs • Radiographic Assessment • Adverse Event (as needed) • Protocol Deviation (as needed) • Patient Discontinuation (as needed)

Interim / Unscheduled Visit	
 • Adverse Event
Study Principle Investigator	

I. INTRODUCTION

A. Purpose

To assess the safety profile and fusion rates following posterior lateral fusion with the *Dynesys*® Spinal System as an adjunct to fusion compared to a literature control.

B. Objectives

Determine the fusion rates at every treated level.

For adverse events at every treated level:

- Determine the incidence rates.
- Determine the severities.
- Determine the time course.

For subsequent surgical procedures at every treated level:

- Determine the types of surgical procedures that are required.
- Determine the incidence rates.
- Determine the time course.

Based on explanted, retrieved devices:

- Determine the failure modes.
- Determine the causes of failure.

C. Study Design

This is a prospective, non-randomized study involving up to 168 subjects at up to 12 investigative centers. Each subject will be an appropriate candidate for an instrumented, pedicle screw implantation and will meet the inclusion and exclusion criteria defined in Section III. Patients will receive either (1) *Dynesys/Dynesys Top Loading* with autograft at the instrumented levels, as an adjunct to fusion, or (2) *Zimmer DTO Implant* with autograft at the instrumented levels, as an adjunct to fusion and will be compared to a literature control.

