- **Removal:** a procedure where the entire original system configuration is removed with/without replacement.*
- **Reoperation:** any surgical procedure at the involved level(s) that does not involve removal, modification or addition of any components to the system.
- **Supplemental Fixation:** a procedure in which additional instrumentation not under study in the protocol is implanted at the spine level(s) under study.

* Elective removals following fusion are not considered adverse events; however, they will still be reported.

All adverse events observed during the course of this study, regardless of severity or relationship to the investigational device will be recorded on the Adverse Event case report form. All events should be followed until resolved or until a chronic, stable state is achieved.

All serious adverse events and unanticipated adverse device effects or events of unexpected severity must be reported to Zimmer Spine within 24 hours of the time the investigator learns of the event or effect. Zimmer Spine will notify the reviewing IRBs within 10 days of the time of learning of the event.

H. Adverse Events Advisory Group

Independent spine surgeons (neuro or orthopedic) will be selected from a subset of 13 member (10 US and 3 OUS) Zimmer Spine Clinical Affairs Advisory Group (CAAG), who are not study investigators, to determine adverse event severity and device relationship.

The CAAG surgeons serve two-year terms and function to provide expert advice to the Clinical Affairs department with respect to protocol development, unmet clinical needs, clinical benefits of devices, quantification and measurement of clinical evaluations, pathology, diagnosis and indication and review of explant cases during clinical trials. The surgeons have a strong core competency in the conduct and logistics of clinical trials. This group allows Zimmer Spine the ability to quickly and responsibly respond to any questions regarding clinical use of our devices, review of data from clinical trials and response to other research collaborators with respect to study conduct. The members of this panel can be trained on the protocol, most importantly, with respect to the blind adjudication of adverse events determining severity and relatedness. The depth of the panel allows

Zimmer Spine to easily convene three members for adjudication and receive expert assistance in review of any adverse events that may ultimately be “unanticipated” or “serious.”

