The adjudication process will occur at least annually during the study. Reviewers will be blinded to the site. Two independent surgeons will review all available appropriate data (including CRFs, AE forms, hospital operative reports, lab reports, films, discharge reports, etc.) and determine:

- whether the event is related to the device, device procedure, general surgery; or none of the above
- AE severity (mild, moderate, severe)
- whether the event constitutes a SAE or UADE.

In instances of non-concordance between the two surgeons, a third surgeon will provide the final determination. The surgeons will provide their review, adjudication and reporting independent of the trial.

All reviewing surgeons' determinations regarding the AEs are final and supersede preliminary judgments made by each clinical investigator.

The sponsor has the responsibility for coordinating the adjudication process. All correspondence, reports, minutes and other documentation as applicable will be supplied to the FDA as part of the regular progress reports.

The sponsor will notify regulatory authorities (FDA, IRB, etc) and the clinical study investigators of any SAE/UADEs in accordance with regulations.

I. Explant Analysis

All hardware segments, complete constructs or components must be returned to Zimmer Spine for analysis by the site using the explant kits provided at the initiation training. Instructions and all necessary materials for returning the hardware will be included in the explant kit. Investigators and external Zimmer representatives will be trained on the importance and process of returning explants for analysis.

Every attempt will be made to evaluate the explanted devices using the Analysis of *Dynesys* Explants Protocol (Appendix A). A secondary analysis to determine the association (if any) between demographics, clinical data, device failure and characteristics will also be completed.

J. Patient Withdrawal

A patient is enrolled in the study by signing a Zimmer Spine, Inc., IRB approved informed consent. No personal health information will be collected from the patient prior to obtaining a signed informed consent.

Patients who are determined to be ineligible prior to surgery will be considered screen failures and will not require additional follow-up visits. The reason(s) for ineligibility will be documented on the Patient Discontinuation case report form.

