Patients who complete the Pre-Operative visit, but do not receive treatment with the study device will be considered discontinued. The Patient Discontinuation case report form will indicate proposed surgery not performed.

Patients have a right to withdraw permission (revoke informed consent authorization). Patients who withdraw consent will have no further private health information collected. Once authorization is revoked, patients may no longer participate in the research activities, but standard medical care will not be affected. Revoking authorization only affects information obtained after the request has been received, but not information obtained prior to that time. Patient withdrawal will be documented on the Patient Discontinuation case report form.

Remuneration will be provided to all subjects who complete scheduled follow-up office assessments at 24 months and annual follow-up visits thereafter as required. The subjects' financial compensation package will be outlined in the Informed Consent Form and approved by the Institutional Review Board (IRB) prior to the start of the study.

Every attempt will be made to contact patients who are non-compliant or lost to follow-up. Three contact attempts by certified letters will be documented. Patients who are lost to follow-up will be documented on the Patient Discontinuation case report form.

To compensate for a potential 20% attrition rate, additional subjects have been added to the sample size. The number of enrolled and completed subjects will be closely monitored, and if needed patients will be added to assure the study endpoints can be achieved.

K. Data Collection

The purpose of the case report form is to reconstruct the study. Information should always be documented in the source document first, and then transferred to the case report form, either paper or electronic. As an exception, the Oswestry Disability Index (ODI) and Patient Assessment forms are considered source documents. It is recommended that patient questionnaires be completed prior to the patient meeting with any clinical staff to minimize the bias in the study or in accordance with site specific standard operating procedures.

Patient confidentiality will be protected at all times and patient identifiers will be used.

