Case report forms must be completed in black ink. To correct an entry, strike a single line through the error and mark the correct response. Date and initial the correction. Do not use liquid paper or correction tape.

Case report forms should be submitted via an electronic data capture system within 15 days of evaluation. Radiographs should be sent via Fed Ex to Zimmer Spine, Clinical Affairs, [name] within two weeks of evaluation.

V. STATISTICAL ANALYSIS

A. Analysis Population

The population for analysis will include all subjects who have completed eligibility screening, signed an informed consent, and have met inclusion and exclusion requirements.

A poolability analysis will be done to ensure that the two Dynesys devices (*Dynesys/Dynesys Top Loading* with autograft at the instrumented levels and *Zimmer DTO Implant* with autograft at the instrumented levels) have similar outcomes. The summary statistics resulting from the primary safety and fusion endpoints, for each subgroup, will be explored to assess possible differences in results based on the subgroup. Additionally, poolability will be assessed by comparing the subgroup population characteristics for key baseline, demographic and clinical characteristics as well as for primary diagnoses. If there are no differences in this comparison, the subgroups will be pooled for the purpose of analysis.

Similarly, a poolability analysis will be done to ensure that there are no differences in outcomes between the different level procedures (1-level, 2-level, 3-level). The summary statistics resulting from the primary safety and fusion endpoints, for each subgroup, will be explored to assess possible differences in results between the subgroups. Additionally, poolability will be assessed by comparing the sub group population characteristics for key baseline, demographic and clinical

characteristics as well as for primary diagnoses. If there are no differences in these comparisons, the subgroups will be pooled for the purpose of analysis.

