Detailed and descriptive analyses will be provided for all adverse events, including specific treatment required and outcomes for all secondary surgeries at the index and adjacent levels, any deaths, and all potential device related adverse events. Adverse event incidence rates, severities and time course will be determined. For subsequent surgical procedures, at every treated level, the type of surgical procedure required the incidence rate and time course will be determined and reported.

¹ Normand, S. T. (1999). Tutorial in biostatistics meta-analysis: Formulating, evaluating, combining, and reporting. *Statist. Med.* (18), 321-359.

All of the safety endpoints will be summarized descriptively at all available assessments. Summaries will be chosen as appropriate for the scale and distribution of the measures being analyzed. For categorical variables, summaries will consist of counts and percentages to describe the distribution of the endpoint. For continuous variables, descriptive summaries will consist of N, Mean, Median, Standard Deviation, Minimum and Maximum. Similarly, exact incidence and rates of AEs and subsequent surgical procedures will be calculated for the experimental group and whenever possible for the control group.

Assessing adverse events (AEs) using only the literature control data is not sufficient, because of the heterogeneity of reporting across the manuscripts. Thus, we propose using the observed data from the recent Dynesys IDE clinical study (historical). The AEs collected in this study (historical) is expected to have a similar profile as those in the present study (experimental). A test for non-inferiority will be performed using both incidence and rates, for each AE category, in both the historical control and experimental group. Non-inferiority will be inferred if the lower limit of the 95% confidence interval around the treatment difference between the 2 groups is greater than $\delta = -10\%$, using the hypotheses below where p_e is the incidence or rate in the experimental group and p_d is the incidence or rate in the historical study group.

$$H_0: p_e - p_d \leq -0.10$$
$$H_1: p_e - p_d > -0.10$$

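### The only analysis population is defined by eligibility rather than implantation, so patient-level adverse event and re-operation incidence may be understated

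*Combined protocol and SAP*

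**What the plan says.** Section V.A (Analysis Population) gives a single definition: "The population for analysis will include all subjects who have completed eligibility screening, signed an informed consent, and have met inclusion and exclusion requirements". I found no safety, as-treated or implanted set elsewhere.

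Section IV.J (Patient Withdrawal) sets the entry point before surgery: "A patient is enrolled in the study by signing a Zimmer Spine, Inc., IRB approved informed consent". It then separates two groups who do not go on to treatment:

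- Ineligible before surgery: "Patients who are determined to be ineligible prior to surgery will be considered screen failures". They have not met the criteria, so V.A already leaves them out.
- Eligible but not implanted: "Patients who complete the Pre-Operative visit, but do not receive treatment with the study device will be considered discontinued". This is a disposition label. Nothing in IV.J or V removes these patients from the analysis.

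Section V.C (Primary Analysis: Safety Endpoints and Evaluation) says that "exact incidence and rates of AEs and subsequent surgical procedures will be calculated for the experimental group", without naming a denominator. The objectives in I.B use a different unit: "For adverse events at every treated level". Section IV.G requires that "All adverse events observed during the course of this study, regardless of severity or relationship to the investigational device will be recorded", so the data are collected whichever set is analysed.

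**The concern.** A surveillance study of a device should count events among the people who were exposed to it. The V.A definition departs from that in two ways.

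First, an eligible, consented patient whose operation does not take place meets every V.A condition. Such a patient adds one to a patient-level denominator and cannot add a device event.

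Second, an implanted patient later found to breach a criterion fails the V.A condition and leaves the population, events included. Late breaches are realistic. Use of an interbody device is an exclusion that can arise at surgery, obesity is an exclusion without a numerical threshold, and the bone density scan in IV.A covers only women over 50.

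At stake are the AE and subsequent-surgery incidence figures, which are main outputs of a study that Appendix A describes as ordered by the regulator. V.C also compares these figures with the literature, article by article, to check that the device does no worse. An incidence that is too low makes that comparison easier to satisfy.

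**Working it through.** The plan states no figure on this point to reproduce. The only related number is the attrition allowance in V.G: 134 / 0.80 = 167.5, rounded to 168. It does not depend on the population definition, but its 20% gives an outer bound for the share never implanted.

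**Inputs.** None of these is in the documents; all are assumptions.

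- p = incidence among eligible implanted patients, taken as 20%
- u = share of the V.A population never implanted
- v = share of implanted patients who breach eligibility
- r = AE risk of breachers relative to eligible implanted patients

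**Formulas, patient level.**

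- Reported under V.A: p × (1 − u)
- All implanted patients: p × (1 − v + v × r)
- The reported figure is too low only if u > v × (1 − r)

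**Dilution alone (v = 0).**

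| u | Reported |
|---|---|
| 2% | 20% × 0.98 = 19.6% |
| 5% | 20% × 0.95 = 19.0% |
| 10% | 20% × 0.90 = 18.0% |
| 20% (all planned attrition before implantation) | 20% × 0.80 = 16.0% |

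**Exclusion of breachers alone (u = 0, v = 5%).** The plan reports 20%.

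| r | All implanted patients | Reported minus all implanted |
|---|---|---|
| 0.5 | 20% × (0.95 + 0.025) = 19.5% | +0.5 points |
| 1 | 20% × (0.95 + 0.05) = 20.0% | 0 |
| 1.5 | 20% × (0.95 + 0.075) = 20.5% | −0.5 points |
| 2 | 20% × (0.95 + 0.10) = 21.0% | −1.0 points |

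**Both (u = 5%, v = 5%).** The plan reports 19.0% against 19.5% (r = 0.5) to 21.0% (r = 2), an understatement of 0.5 to 2.0 points. At r = 0.5 and v = 5% the condition is u > 2.5%. At r = 0.5, v = 10% and u = 5%, the two errors cancel (19.0% against 19.0%).

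**Treated-level rates.** A never-implanted patient has no treated level and adds nothing to that denominator, so no dilution occurs. The removal of implanted breachers still applies.

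**Effect on the two AE comparisons in V.C.** Against the earlier Dynesys study, the criterion as written needs the lower 95% limit of p_e − p_d to exceed −10%. Lowering p_e from 20% to 19% moves the difference one point towards −10%, so the criterion becomes harder to meet. Against the literature, the experimental incidence should not exceed what was published, so a lower figure helps.

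**Fusion.** Under V.B, a subject with no Month 24 status and no earlier fusion leaves the primary analysis, so never-implanted patients drop out there. The V.B sensitivity analysis then counts those same subjects as not fused. As an illustration, if every implanted subject had a determined status and 80.6% were fused, u = 5% would give 80.6% × 0.95 = 76.6%, a fall of 4.0 points that has nothing to do with the device.

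**The case against.** The strongest reply is that other text already limits the damage.

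- *Never-implanted patients are identified separately and fit no analysis.* They have their own disposition entry, no treated level, and no place in the poolability groups by device or number of levels. V.F drops unavailable values from summaries. This has some force, and it holds for treated-level rates. It does not settle a patient-level incidence: a patient without an AE form is counted as having no event rather than as having a missing value, and V.C does not say who is counted.
- *No text tells the analyst to delete an implanted breacher.* Eligibility could be read as judged once, at the pre-operative checklist. That is a possible reading, but V.A requires that the criteria were met, and nothing brings back a patient for whom this proves untrue. Recording every AE, and describing all of them as V.C promises, does not put that patient into the incidence figure.
- *The size is small and assumed.* This stands. The illustrated error of 0.5 to 2.0 points is modest beside the 10-point margin in V.C.

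A reader might go further and infer that incidence is certain to be understated. The documents do not support that. Dilution needs such patients to exist and a patient-level denominator that counts them. Exclusion has no fixed direction unless breachers are at higher risk. The Dynesys instructions for use call obese patients, those who abuse alcohol and those with poor bone quality poor candidates for fusion, and the OPTIMA ZS instructions link obesity to fixation and device failure. That points to r above 1 for some criteria but puts no number on it.

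A reader might also infer that the definition helps the device pass the comparison with the earlier Dynesys study, or that it compromises the primary fusion result through never-implanted patients, or the explant work. The first runs the other way as the criterion is written. Never-implanted patients already leave the primary fusion analysis. Appendix A, section 4.1, covers all retrievals received, whatever the analysis population.

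**Conclusion.** The defect is in the stated rule: V.A admits patients without exposure and shuts out some with exposure, and no safety set corrects this. Its consequence is conditional. Patient-level AE and re-operation incidence may be understated. With 20% incidence in eligible implanted patients and 5% for each share, the reported 19.0% compares with 19.5% to 21.0% in all implanted patients for risk ratios of 0.5 to 2. All of these inputs are assumptions, and other values can give no net error or one in the opposite direction. Never-implanted patients do not affect treated-level rates. A lower figure eases only the literature comparison. In the fusion sensitivity analysis, never-implanted patients would be counted as failures. The effect is probably modest, but it falls on a main safety output and can be removed with wording.

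**What to change.** In V.A, define a safety set of all subjects in whom implantation of the study device was performed or attempted, regardless of eligibility deviations. Including attempts keeps intraoperative events in the count. Then:

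- use this set for all AE and subsequent-surgery incidence in V.C, and name the patient and treated-level denominators;
- report never-implanted subjects in disposition only, and leave them out of the fusion sensitivity analysis in V.B;
- report the eligibility-compliant subset as a sensitivity analysis.

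The cost is a change of wording before analysis. No new data are needed, because IV.G already requires all AEs to be recorded. The downside for the sponsor is that AE figures may be slightly less favourable.

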To assure that baseline characteristics of the history control data are similar to those found in the experimental data, the demographic characteristics from the study data will be reviewed to confirm that the characteristics of age, gender, smoking status, and preoperative diagnosis in the test data are similar to the data that existed for the historical control data. The rate of males and rate of smokers will be checked against the 95% confidence interval found in the point estimate table. The distribution of preoperative diagnoses will be tested for no difference between the historical control and the test group. The average age will be checked to assure that it is in the range from 41 to 75. If any differences are noted, patients with extreme data will be removed until the rates and means of the test population do reside within the bounds determined by the meta-analysis. If needed, more patients will be enrolled in the test group to assure that the sample size is sufficient for inferential testing.

B. Primary Analysis: Fusion Status

Fusion success will be defined as evidence of bridging bone and angulation of <5° and translation of <3mm at treated levels at 24 months. Radiographic assessment will determine for each patient a fusion status, either fused or not fused. The primary endpoint is fusion status at Month 24. Efficacy will be confirmed by the achievement of fusion in the experimental group when compared to the rate established in a literature control. Normand (1999) provided the direction for the meta-analysis¹. The details of that analysis included creating population mean and variance estimates using a weight of the inverse of the variance. (See pp. 335-336 for complete description of the algorithm) A point estimate of 80.6% with a standard error of 2.6% was established. The 95% confidence interval for this point estimate is (75.0%, 86.3%).

If Month 24 fusion status cannot be determined, but fusion was determined to have occurred earlier, the Month 24 status will be considered fused. Otherwise, subjects without earlier fusion who are missing Month 24 values will be excluded from primary analysis.

For the purpose of a sensitivity analyses, all subjects excluded as described above for a missing Month 24 fusion status will be defined as not fused.

C. Primary Analysis: Safety Endpoints and Evaluation

Subjects will be clinically evaluated for adverse experiences and functional outcomes over the course of 24 months.

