Removal and Refusion				

E. Baseline and Operative Analysis

Baseline summaries will be chosen to be appropriate for the scale and distribution of the measures being analyzed. Statistical methods will be the same as described above for the non primary endpoint analyses.

F. Missing data

Except for the primary analysis, if a value, at any assessment is not available for analysis, it will be excluded from summaries.

G. Study Hypothesis and Sample Size Determination using a Literature Control

Study Hypothesis

The hypothesis is Dynesys fusion rate is non-inferior to the historical literature sample data estimated fusion rate of 80.6%. This hypothesis will be assessed by testing that the difference between the experimental rate (p_e) and the historical control rate (p_c) is not worse than 10%. The non-inferiority test will be inferred if the lower limit of the 95% confidence interval around the **treatment difference** between 2 groups is greater than $\delta = -10\%$.

$$H_0: p_e - p_c \leq -0.10$$

$$H_1: p_e - p_c > -0.10$$

Sample Size

Sample size for the Dynesys Post-Market Surveillance Study was estimated using SAS, Proc Power with a testing level alpha (Type I) error level of 0.05, 80 percent statistical power, a meaningful difference of 10%, and a success rate for lumbar fusion from the literature historical

control group of 80.6% (0.806). For this set of criteria, the sample size was 134, without adjustment for attrition. With a 20% attrition sample added, this would result in a sample size of 168.

Sample size estimates are presented in Table 2.

Table 2: Proposed Sample Sizes

Primary Endpoint	Difference	Predicted Success	Type I Error	Power	N Patients
Radiographic Success (Fusion)	10%	80.6%	0.05	80%	168

VI. TIMELINE

A. Clinical Trial Agreement

No portion of this protocol will be implemented until both copies of the Clinical Trial Agreement have been completed by both parties.

Table 3: Study Timeline

Study Timeline	Sponsor Expectation
Expected date of Study Initiation	March 2012
Expected date of first IRB Approval(s)	January 2012
Expected monthly number of sites obtaining IRB approval	1
Expected subject enrollment initiation	March 2012
Expected average number of subjects to be enrolled/month	7
Expected Date of Subject Enrollment Completion	March 2014
Expected date of Subject follow-up Completion	March 2016
Reports	
Interim Postmarket Surveillance Study Report	Every 6 months through 2 years, annually thereafter

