Re-insert the optional *Dynesys Guide Pins* on the *Dynesys* screws heads to assist in docking instrumentation.

Using the *Dynesys Pedicle Distance Gauge* with a forked edge, measure the spacer length between the *Dynesys* pedicle screw and the *OPTIMA ZS* transition screw.

Verify that the Drag Indicator is in the start position.

Assess the movement in the facets in distraction and compression. Measure the distance (spacer length) with a slight distraction force.

Note: The Pedicle Distance Gauge with a forked end must be used, and is included in the DTO instrument tray.

Caution: Do not induce kyphosis or scoliosis.

Record the measured spacer length for the levels.

[figure not shown]
Cut the *Dynesys* spacer with the *Dynesys Spacer Cutter* according to the previously determined measurement.

Thread the appropriately sized spacer onto the *DTO* cord and place against the *OPTIMA ZS* transition screw head.

Using a clamp, insert the *DTO* cord through the *Dynesys* pedicle screw head.

Note: The end of the introduction zone of the cord can be bent to facilitate the introduction of the cord into the screw head.

Note: Avoid twisting and looping of the cord.

[figure not shown]

Top View of Pedicle Distance Gauge

Complete the *Dynesys* construct assembly and cord tensioning according to the *Dynesys* LIS Surgical Technique, L1301:

- Construct Assembly

Final Construct

After segment by segment work, a two-level assembly is completed.

Decorticate the posterior elements as necessary. Place bone graft to achieve the desired fusion.

Hardware Removal/ Revision Instructions

Set Screw Removal

Position the appropriate Anti-Torque Device over the pedicle screw body of the set screw to be removed. Insert the matching Torque Wrench through the Anti-Torque Device and into the set screw. Turn the Torque Wrench counterclockwise until the set screw is loose but not completely disengaged. Remove the Torque Wrench and Anti-Torque Device. Carefully remove the *OPTIMA* ZS set screws with the Set Screw Driver Guide and the *Dynesys* set screws with the Set Screw Starter. Repeat for all set screws.

DTO Implant Removal

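### Number of treated levels is left out of the comparison with the literature and is tied to device type, so level mix could shift the fusion result and the DTO comparison by an amount the plan cannot detect

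*Combined protocol and SAP*

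**What the plan says.** **Endpoint.** Section V.B defines fusion success as "evidence of bridging bone and angulation of <5° and translation of <3mm at treated levels at 24 months" and assigns each patient a single status, fused or not fused. The Imaging Protocol (V.E, Fusion Status) grades each treated level separately. No section says how level grades combine into a patient status.

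**External comparison.** Section V.A asks whether "characteristics of age, gender, smoking status, and preoperative diagnosis in the test data are similar to the data that existed for the historical control data". Number of levels is not on that list, and the table of articles has no column for it. Neither V.A nor V.B says whether the 80.6% literature rate counts patients or levels.

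**Checks inside the trial.** Section V.A plans one poolability analysis of the two devices and, separately, another to ensure that "there are no differences in outcomes between the different level procedures (1-level, 2-level, 3-level"). Subgroups are pooled if no differences are seen. There is no numerical criterion, and nothing is said about what follows if subgroups differ.

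**Device.** Section II.A requires the DTO implant when Dynesys and OPTIMA ZS are used on contiguous levels. The Instructions for Use (1.0 Description) call it the interface between the two systems at adjacent levels. The DTO surgical technique describes the same use and closes its worked example with "After segment by segment work, a two-level assembly is completed".

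**The concern.** If all treated levels must fuse, a three-level patient has to succeed three times and a one-level patient once. The trial's patient-level rate then depends on its level mix as well as on the device, and so does the literature rate if it counts patients. The plan regards level count as important enough to check within the trial, but does not carry it to the external comparison on which the primary conclusion rests. A trial with more multilevel cases than the articles could miss non-inferiority with a sound device; the opposite imbalance could hide a worse one.

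The second problem is internal. A DTO patient cannot be a one-level patient. The device check is therefore partly a comparison of level counts, and running the device and level checks one at a time cannot separate the two. The device check decides whether the devices are pooled.

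**Working it through.** **1. The plan's own figure.** Section V.G: "control group of 80.6% (0.806). For this set of criteria, the sample size was 134, without adjustment for attrition". With z = 1.960 and 0.842, [1.960·√(0.806·0.194) + 0.842·√(0.706·0.294)]² / 0.10² = 134.2, matching 134. Then 134/0.8 = 167.5, so 168. Both figures reproduce, and 134 is used below. (This formula has 0.806 as the null and 0.706 as the alternative. Exchanging them to fit the stated hypotheses gives 150.2, so 151; that is a separate matter.)

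**2. Inputs.** From the documents: 80.6%, the 10-point margin, the 95% confidence-interval rule and N = 134. Not in the documents, so assumed: the level mixes of the trial and the literature, the per-level fusion rate q, and the within-patient correlation ρ. All results below assume that all treated levels must fuse.

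**3. Formula.** For k levels, P(all fused) = q^k if levels are independent. With correlation ρ, using the beta-binomial, it is the product over i = 0,…,k−1 of (qM + i)/(M + i), where M = 1/ρ − 1.

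**4. Shift against the literature, taking 80.6% as a single-level (or per-level) rate.** The assumed trial mix is 50/40/10 for 1/2/3 levels.

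| ρ | 1 level | 2 levels | 3 levels | 50/40/10 mix | Shift (points) |
|---|---|---|---|---|---|
| 0 | 80.6% | 65.0% | 52.4% | 71.5% | −9.1 |
| 0.3 | 80.6% | 69.7% | 62.4% | 74.4% | −6.2 |
| 0.5 | 80.6% | 72.8% | 68.1% | 76.2% | −4.4 |

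First row: 0.5·0.806 + 0.4·0.650 + 0.1·0.524 = 0.715.

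**5. The same trial mix when the literature also has multilevel cases**, with q reset so that the literature mix gives 80.6% per patient:

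- Literature 80/20/0: −5.3 (ρ = 0), −3.7 (0.3), −2.7 (0.5).
- Literature 60/30/10: −1.2, −0.9, −0.7.
- Literature 60/30/10 with a trial mix of 70/25/5: +1.7, +1.2, +0.9. The sign reverses.

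Over trial mixes from 70/25/5 to 0/80/20, literature mixes from 100/0/0 to 60/30/10, and ρ from 0 to 0.75, the shift runs from about +2 to −18 points.

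**6. Effect on power.** With 134 evaluable, the benchmark taken as fixed and no true device deficit, power = Φ[(p − 0.706)/√(p(1−p)/134) − 1.960].

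- No shift, p = 0.806: 0.100/0.0342 = 2.93, power 83%.
- −3 points, p = 0.776: 0.070/0.0360 = 1.94, power 49%.
- −5 points, p = 0.756: 0.050/0.0371 = 1.35, power 27%.

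**7. Device comparison with no device effect.** Assumed mixes are 50/35/15 for Dynesys and 0/70/30 for DTO.

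- q = 0.90, ρ = 0.3: success is 90.0/83.7/79.2% for 1/2/3 levels. Dynesys is 86.2%, DTO 82.4%, a difference of 3.8 points.
- Range: 8.0 points (q = 0.85, ρ = 0) down to 1.1 (q = 0.95, ρ = 0.6).
- Restricted to two or more levels, Dynesys 35/15 becomes 70/30, the same as DTO, and the difference is zero. If the restricted mixes differed, stratifying by level count would deal with the rest.

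**The case against.** Four points on the other side deserve weight.

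- **The all-levels rule is not written.** A reader might take V.B to say that every treated level must fuse. It says only at treated levels; the visit sections (IV.C to IV.E) speak of overall and unilateral fusion, and the objectives ask for rates at each level. The reading is natural, but the defect in the text is the missing rule. This stands, and every magnitude above depends on that reading.
- **A reader might infer that surgical mix alone moves the result by about the 10-point margin.** The documents do not support that. They give no level mix, and do not show that the literature's mix differs from the trial's. Among the scenarios run, about −10 needs weakly correlated levels, a mostly single-level literature and about half or more multilevel cases. With moderate correlation or similar mixes, the shift is about 0 to 6 points.
- **Levels are not ignored.** V.A already requires fusion summaries for 1-, 2- and 3-level patients. That covers the within-trial description, but not the comparison with the articles. The articles may not report levels: V.A notes that baseline estimates were made only where data sufficed.
- **A reader might infer that the DTO comparison must mislead.** It is exploratory and imprecise. With 134 patients split equally at 84% success, the 95% interval is ±1.96·√(2·0.84·0.16/67) = ±12 points, so a 3.8-point artefact would usually be lost in noise. That limits the harm but does not make the comparison interpretable.

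**Conclusion.** The concern holds in a limited form. On the text alone, number of levels is absent from the literature comparison, the unit of the 80.6% is unstated, no level-to-patient rule is given, and every DTO patient has at least two levels, so device and level count are confounded in the poolability checks.

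The size is conditional. With 80.6% as a single-level rate and a 50/40/10 trial mix, patient success falls by about 9 points (independent levels) to 4 (correlation 0.5). The fall shrinks towards zero, or reverses, as the literature's mix approaches or exceeds the trial's, so the direction is unknown. The shift need not reach the margin to matter: 3 points would roughly halve the chance of meeting the criterion with a device that has no true deficit. The artefact between devices is 1 to 8 points under the assumed mixes.

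**What to change.** 1. **Section V.A, device poolability.** Compare DTO with Dynesys only among patients with two or more levels, stratified by level count. Operative levels are already on the Operative/Discharge Evaluation form. The cost is precision, because one-level Dynesys patients drop out of this comparison.
2. **Section V.B.** State how level grades combine into a patient status. Extract the number of levels and the unit of the fusion rate from the articles already in hand, and compare the trial with 80.6% on the same unit.
3. **Beside the primary result**, report fusion for 1-, 2- and 3-level patients against matching literature strata, or against a benchmark re-weighted to the trial's level mix, where articles report levels.

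Use level count only to stratify or standardise. It should not simply be added to the V.A comparability list, because that section responds to differences by removing patients with extreme data, and removing patients by level count would introduce selection.

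The cost is re-reading the articles and a few extra tables; no visit, treatment or enrolment target changes. Some articles may not report levels. The strata would then be incomplete, and the report should say so.
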